As an exploratory analysis to assess for feasibility in preparation for a phase 2 trial, the U of M research team will apply MPOWER guidelines (regarding fat, fiber, sugar and calorie content) to assess whether students' food choices in week 4 were healthier than those in week 1 using the uploaded photos, accompanying student annotations, and nutrition information from venues' menus. We also will explore any associations between changes in food choice and student characteristics (i.e., sex, level of interest in making changes, BMI).

C.4. Project Timeline by Month

Project Activity	1	2	3	4	5	6	7	8	9	10	11	12
Aim 1												
Requirement planning and use case design	X	X		X								
Iterative Development (smartphone and server /web-service tools)		X	X	X	X	X						
Prototype mobile application and server						X	X					
Aim 2												
Collect menus and identify healthiest options	X	X	X	X								
Develop questionnaires, interview guides, and focus group prompts	X											
Recruit cultural tailoring focus groups		X	X									
Cultural tailoring focus groups			X	X								
Adapt and culturally tail messages				X	X							
Recruit message testing groups				X	X							
Message testing groups						X						
Revise messages						X	X					
Aim 3 - Pilot Testing and Reports												
Recruit for pilot							X	X	X			
Pilot study								X	X	X		
Data analysis and reporting									X	X		

the most robust services available, including augmented GPS, cellular triangulation and local RF (e.g., WiFi). An outcome of this Phase 1 will be to assess our ability to detect eating locations. However, for critical locations, such as a school cafeteria, we will be able to augment the current Google location database if failures are detected. The solution is simply to place a \$15 WiFi transmitter anywhere in the eating venue and register its unique “MAC” address with Google. The transmitter would be recovered at the end of the study. The transmitter will not be connected to the internet. More RF sources are being “discovered” and entered in the Google and similar databases constantly, so we expect that by the time Phase 2 work begins supplemental marking devices will not be needed. In any human research there is always the possibility of difficulty in recruiting. However, 3 schools have agreed to be trial schools. Further, in past studies, we have found adolescents are enthusiastic about participating.

C.6. Commercialization

The ActiPal and PiLR Healthware systems are used in a wide variety of healthy messaging applications, from smoking to weight management and clinical pain control. Once the present methodologies have been developed and proven through an RCT by the University of Michigan and MEI, it will be moved to primary markets, including health and wellness centers, obesity clinics, and corporate wellness programs. This academic and small business collaboration will lead to the development of a sophisticated evidence-based tool likely to aid in reducing health disparities by promoting healthy choices among AA adolescents, and which will be marketable to address this and other situations where timely location-linked messaging may be helpful.

C.5. Limitations / Potential Problems / Alternative Strategies

For the benefit of cost and time, we will build the Phase 1 system with readily available and free Google services combined with our existing ActiPal objective data / EMA applications. Both require the Android operating system (OS). Android is currently the most popular smart device OS so we expect at least half of the students will have a compatible device. Students who do not own a smart device may be issued one for use in the study. In Phase 2 we will extend the system to Apple (iOS) and other OS popular at that time. iOS is not economical to implement in Phase 1 due to commercial distribution restrictions applied by Apple Corporation.

The Google location API combines all of

References

1. CDC Body Mass Index: BMI for Children and Teens. <http://www.cdc.gov/nccdphp/dnpa/bmi> . , 2013.
4. Dietz WH. Health consequences of obesity in youth: childhood predictors of adult disease. *Pediatrics*. Mar 1998;101(3 Pt 2):518-525.

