Our clinical and research experience suggests that tailored texts linked to location will improve choices. *Our clinical work* in the Michigan Pediatric Outpatient Weight Evaluation and Reduction (MPOWER) program suggests that an intervention based on Self-Determination Theory that uses motivational interviewing to increase motivation is effective, but adolescents' success with making healthy choices is greatly impacted by their school environment. *Our preliminary research* in the MPOWERed Messages intervention, incorporating the theories used in MPOWER, indicated that adolescents welcomed individually relevant health-related texts that used social marketing and provided cues to action. Importantly, they believed the texts helped them make healthy choices but suggested it would be better if they were sent at times when they faced dietary choices.

Proposed Intervention: The LIITA³H intervention will include 3 components: 1) **Personal Geo-location mobile technology** to identify when students are in their school cafeteria or other eating venues with an "intent to eat"; 2) **Culturally and individually tailored text messages** to promote healthy choices in these venues; and 3) **Messages delivered** to students when they are in eating locations and a mechanism for them to respond with information about their eating experience such as an annotated photo of their selection.

Hypothesis: We hypothesize that the LIITA³H intervention can be developed to automatically and accurately send text messages, tailored to recipients' preferences /characteristics, when they are making selections in their school cafeteria or other eating venues, and that these health-focused messages will encourage healthy choices.

We will accomplish the following 3 specific aims:

Aim 1: To develop an integrated mobile phone application that will a) accurately identify when students are in their school cafeteria or other eating venue, b) automatically deliver a tailored text message that prompts healthy choices, and c) receive a photo of food choices annotated with the user's health rating of the food. [For this amendment we aim to optimize the previously developed app to automatically identify a larger number of fast food restaurants (FFR) using GPS monitoring and by incorporating additional user input regarding the app design]

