Message Testing Groups. A sample of the

adapted texts will be tested with the target population (2 groups with 6 to 8 students/group). Population, recruitment and consent/assent as above. Based on methods used successfully in our prior studies, students will use an OptionFinder audience response handset³⁴ to indicate for each text if they: (1) Really liked it = No Changes, (2) Thought it was O.K. = Improve, or (3) Did not like it = Reject. Messages with $\geq 60\%$ "really liked" and those with 60% "did not like" rating will be viewed as a consensus and not discussed further. All others will be discussed to elicit suggestions for improvements. The research team has extensive experience with testing and revising text messages for use in behavioral interventions. Students will receive a \$25 gift card for participating in this 2-hour group. [For this amendment, message testing groups will be replaced with a 5 – 10 member adolescent advisory board recruited. Key informants from the community (e.g., teachers our previous studies) will be asked to provide recommendations for possible members, and adolescents will also be selected from participants in the focus groups. The PM will contact the parents to describe the board. If they give verbal consent for their adolescent to participate, teens will be contacted to discuss the study and to assess their interest. Signed consent/assent will be obtained at the first meeting. Teens will receive a \$50 incentive per month of participation.

For convenience, these 90 minute meetings will be held in Detroit, Flint and Benton Harbor, and attendance via Skype or VSee teleconferencing will be offered. Meetings will be facilitated by the PI who works extensively with adolescents in clinical and research settings.

Tailored Menu Recommendations. Additional menus will be obtained from schools and popular fast food venues. The healthiest options will be identified from each venue for a variety of categories (e.g., salty foods, dairy

Table 1: MPOWERed Messages Library Message Types		
Message Type	Description	Example
Testimonials	Strategies others found helpful in weight loss	A teen says "TV was one of my favorite things, and I really didn't want to cut back. But, I dropped a few shows, and the truth is, I don't even miss them!"
Reflective Questions	Prompts to consider self-generated ideas	"What does being healthy mean for you? How does screen time fit with your goals?"

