Tailored Messages	Created to be tailored to participants' responses on baseline questionnaire.	Someone who eats breakfast daily might receive the message: "You eat breakfast every day. That's really smart. It means you're less likely to overeat later, especially at lunch. Keep up this great habit!"

foods, etc). The lists will be used to offer recommendations based on users' location and preferences (e.g., in McDonald's a student who said they like dairy foods on the baseline survey, might be asked to try a parfait). Following completion of Aims 1 and 2 the LIITA³H system (Figure 3) will be ready for pilot testing.

[figure not shown]
C.3. Pilot Trial (Aim 3)

We will study the feasibility, acceptability and use of the LIITA³H system via a pilot with four 1-week phases. [This amendment will test the app impact on frequency of visits to, and calories purchased from, FFR in a 6-month pilot].

We have shortened our study period time frame from 6 months to 1 month due to the COVID-19 pandemic.

C.3.a. Population and Recruitment. We will recruit 150 13-17 year olds, with a BMI>85th percentile who eat at FFR at least 3 times/week) from each of the 3 cities. Recruitment and consent/assent are as above. Students will receive two \$30 gift cards as an incentive for participation. A cell phone will be provided for those who do not own one. Payment will also be provided to cover the costs of internet access for those who need it.

Due to the COVID-19 situation that hampers physical contact, recruitment for the research study trial (to replace the in-person enrollment sessions due to the COVID situation) will be conducted virtually through UMHealthResearch.org and through a Facebook and Instagram advertising campaign managed by MICHRA and linked to our UMHealthResearch study page.

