Intervention Group 1 – Participants will be asked to keep the app running on their phone. They will receive a ping when the app identifies that they are in a fast food restaurant followed by a point of purchase prompt, tailored to their preferences and the options available at that location. If they are in a venue without a menu, general healthy suggestions will be provided (such as “consider choosing smaller portions” or “does this venue sell fruit?”). If the app does not ping when they enter a restaurant, they will be asked to register that location by tapping the ‘register location’ button on the app and entering the restaurant name. For detection errors, the appropriate stored venue criteria (location, geo-fence, time of day or dwell time) may be adjusted to improve detection. Users will also be asked to take a picture of any items they buy and to annotate it with information that would help to determine the nutrients in the food. Annotations may be audio, text, or made from a selection of descriptive buttons (e.g., to indicate small, medium or large sizes).

Control Group 2 – Participants in Control Group 2 will receive similar instructions to those given to group 1, but without receiving point of purchase prompts.

Control Group 3 – The Location Only Control Group 3 will only get information about location detection, and asked to register FFR if the app does not indicate with a ping that they have entered one. Their instructions will not discuss photo documentation of food or prompts as these features will not be active on their app.

During the study period, the participants will be contacted once per month by a research team member. Monthly calls will be added to help gather feedback from participants about the app. Study participants will be contacted by phone on three separate occasions, at times when the participants are not in school (e.g. after 4pm on weekdays or a weekend). If, for any reason, a research team member is unable to reach a study participant after three attempts, we will connect with the parent and/or research liaison (e.g. a staff member at the school or community organization we are working with) for assistance.

C.3.d Post Intervention Assessment

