Based on students' responses when using the system we will determine 1) the percentage of the time that the system accurately identified presence in an eating venue and correctly identified the registered venue (cafeteria vs. convenience store), and 2) the percentage of time that an appropriate and relevant message was delivered.

For this amendment, calories purchased will be assessed using submitted annotated photos, and nutrition data from FFR menus (e.g., if the participant submits a picture of McDonald's fries and indicates it is a small order, then from the McDonalds menu, we will determine that the calories purchased were 240 kcals). Frequency of visits will be obtained directly from the app. We will use population averaged generalized estimating equation regressions (GEE) to compare trajectories of calories purchased and number of visits between groups. The GEE approach allows us to account for the correlation in repeated observations collected from each subject over time. For calories purchased, we will perform GEE linear regression modeling as a function of time, treatment group (intervention vs. control group 2) and the interaction of time by treatment group ($Y = \beta_0 + \beta_1 Time + \beta_2 Treatment + \beta_3 Time * Treatment + \epsilon$). Similarly, for the number of visits, we will fit a GEE Poisson regression model as a function of time, treatment group (intervention vs. control group 2 vs control group 3) and the interaction of time by treatment group. Residual diagnostics will be performed to examine departures from model assumptions. If necessary, we will use transformed outcome variables and refit the models.

Secondary Outcome 1 – Acceptability of the intervention and the messages

From the post-pilot interviews we will identify students' perceptions of the intervention overall and of the messages specifically. We will explore opinions of school personnel on impacts of using the LiTAH at school. Data from post-pilot interviews plus the advisory board input, will inform revisions of the app and planning for a larger trial.

For this amendment, we will use the models discussed above to examine associations between calories purchased /number of visits including as covariates participant characteristics such as extent of app use, initial BMI, and ethnic identity (as an ordinal measure assessed via the Multiethnic Identity Scale) as a secondary outcome.

Secondary Outcome 2 – Exploration of food choices

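### The hypothesis concerns healthy choices, but the only randomised comparison of what is chosen is calories purchased; the four-criterion food-quality analysis has no group contrast

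*Combined protocol and SAP*

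**What the plan says.** - **Hypothesis (Specific Aims).** The stated expectation is that "these health-focused messages will encourage healthy choices".
- **What a prompt contains (C.2.b, Tailored Menu Recommendations).** "The healthiest options will be identified from each venue for a variety of categories". As an example, "a student who said they like dairy foods on the baseline survey, might be asked to try a parfait". No criterion for healthiest is given there. Nothing requires the item to be lower in calories than the usual purchase, or to replace another item.
- **Who receives it (C.3.c, Intervention Group 1).** A ping on entering a restaurant is "followed by a point of purchase prompt, tailored to their preferences and the options available at that location". For other venues, "If they are in a venue without a menu, general healthy suggestions will be provided". Control Group 2 gets similar instructions without prompts. Group 3 has no photo feature.
- **What is compared between groups (C.3 and C.3.e).** The amendment will "test the app impact on frequency of visits to, and calories purchased from, FFR". "For calories purchased, we will perform GEE linear regression modeling as a function of time", group and their interaction, for the intervention against Control Group 2. Visits are compared across all three groups.
- **Food quality (C.3.e, Secondary Outcome 2).** MPOWER guidelines on fat, fiber, sugar and calories are applied to the photographed choices. This is exploratory, sets week 4 against week 1, and names no comparison between groups.

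**The concern.** Visits do not show what was bought, so calories purchased is the only randomised evidence on choice. The messages aim at something broader than calories, and the project's own food scoring is broader too. A participant who takes the suggested item in place of one with similar calories but more fat or sugar has done what the hypothesis predicts, and the calorie model records nothing. If the item is added to an unchanged order, calories rise.

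The pilot is meant to inform a larger trial of effects on behavior. If the calorie comparison is flat, the planned between-group analyses cannot show whether purchases also stayed the same in quality or improved in ways that calories do not register. The one planned analysis that could speak to this is a before-after contrast without a control group.

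**Working it through.** The plan states no sample-size calculation, power, effect size or standard deviation, so there is no figure to reproduce. The main check is a comparison of the text.

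**1. Coverage.** The guideline criteria are fat, fiber, sugar and calories. Between-group analyses of choice cover calories only, so three of the four are never compared between randomised groups. The amendment's covariate models under Secondary Outcome 1 again use calories and visits.

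**2. Does week 4 against week 1 fill the gap?** In the original four-phase pilot (C.3.c), tailored messages started in week 3, so week 1 preceded any prompt. Under the amendment weeks 1 to 3 are not repeated, and no unprompted lead-in is described for Group 1. Week 1 is then already a prompted week in that group. Any change from week 1 to week 4 is mixed with time, growing familiarity with the app, and changes in which purchases participants photograph. The other two outcome headings in C.3.e carry an amendment paragraph and this one does not, so it may be carried over from the earlier design. If so, the amended trial has no food-quality analysis at all.

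**3. Can calories move differently from the prompted behavior? (Illustration.)** Let k be the calories of the suggested item, 240 kcal the item displaced, and q the share of followers who swap rather than add. The 240 kcal is the small fries in C.3.e, given there only as a coding example. All k values are assumed.

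- Mean change per followed prompt = k − 240q. Break-even: q = k/240.
- k = 100: 100/240 = 42%. k = 150: 150/240 = 62.5%. k = 200: 200/240 = 83%.
- With k = 150 and half of prompts followed (assumed), the change per prompted visit is 0.5 × (150 − 240q): −45 kcal if all swap, +15 if half swap, +75 if all add.

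**4. Could the calorie comparison detect this? (Illustration.)** Assumed: two-sided alpha 0.05, visit-level SD 300 to 500 kcal, within-person correlation 0.3, equal allocation, and a simple difference in means rather than the planned time-by-group interaction. From the plan: at least 3 visits a week, about 12 in one month. The 150 recruits give 50 per arm if that is the total, or 150 per arm if it means 150 from each of three cities.

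- SD of a participant's mean = SD × √[(1 + 11 × 0.3)/12] = SD × 0.599, giving 180 to 299 kcal.
- Standard error of the difference at 50 per arm = that × √(2/50) = 36 to 60 kcal.
- Power = Φ(|difference|/SE − 1.96).

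| Difference | 50 per arm | 150 per arm |
|---|---|---|
| −45 kcal (all swap) | 11–24% | 25–58% |
| +15 kcal (half swap) | 4–6% | 6–11% |

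**5. Sensitivity.** If the displaced item is 400 kcal (assumed) and all followers swap, the change is 0.5 × (150 − 400) = −125 kcal, and power at 50 per arm is 55% to 94%. If half swap, it is 0.5 × (150 − 200) = −25 kcal, and power is 6% to 10%. The answer depends heavily on inputs the documents do not supply. Steps 1 and 2 do not depend on them.

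**The case against.** The strongest reply is that the outcomes match the aim. Amended Aim 3 asks about fewer calories purchased and fewer visits, and the analyses test exactly those. For adolescents above the 85th BMI percentile, calories are a defensible endpoint. A participant who adds a suggested item to an unchanged order has bought more calories, and the model would rightly say so. This stands: calories should stay, and an added item should not be called a success.

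Second, other data bear on whether prompts were followed. The system records compliance with prompts, the EMA questions ask whether a text influenced the choice, and the interviews cover choices made. A reader might infer that the trial cannot tell whether prompts were followed, or that a flat calorie result means the whole trial reads as no effect. The documents support neither, since visits, feasibility and acceptability are also assessed. But none of these sources is a stated randomised comparison of the quality of purchases.

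Third, the menu item is an example of tailoring, not a fixed rule. The library also holds testimonials and reflective questions, and general advice may suggest smaller portions, which acts on calories directly. Calories may also weigh in what counts as healthiest. This stands, and it is why the divergence is possible rather than certain.

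Fourth, a reader might want uptake of the suggested item, Group 1 against Group 2, to decide the hypothesis. The plan does not support that. It defines no deterministic rule fixing the item for each participant and venue, so the item for an unprompted participant cannot be derived reliably. Group 1 could also photograph compliant purchases more readily, which would inflate uptake.

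**Conclusion.** The point holds as a gap in the analysis plan, not as a fault in the calorie outcome. Three of the four criteria by which the project judges food are never compared between randomised groups, and the one analysis that uses all four is a before-after contrast whose first week is no longer free of prompts. This rests on the text alone, on the reading that no unprompted lead-in applies to Group 1.

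A prompt that is followed could leave the calorie comparison unchanged or move it upward. How often is unknown. The break-even shares (42% to 83%) and power figures are illustrations on assumed inputs, and a larger displaced item improves the calorie comparison's chances considerably. A reader might infer from the low power figures that calories are bound to miss the effect. The documents give no item calories, SD or effect size from which to conclude that, and low power for a small difference is largely a matter of sample size.

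**What to change.** In C.3.e, Secondary Outcome 2, replace or supplement the week 4 against week 1 contrast with a Group 1 against Control Group 2 comparison of the MPOWER-guideline score per photographed fast food purchase:

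- Use the same GEE approach as for calories.
- State how the four criteria are combined into a score.
- Label the comparison exploratory.
- Report photo-submission rates by group beside it. Visits recorded automatically by the app can serve as the denominator.

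Keep calories and visits as planned. Uptake of the suggested item may be described within Group 1, as a check that prompts were followed, but should not decide the hypothesis.

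The cost is one more exploratory outcome, SAP wording and a little more coding; photos, menus and guideline scoring are already planned. Group 3 submits no photos and cannot be included. Randomisation removes the time confounding, but selective photo submission may still differ between the groups, which is why the submission rates must accompany the result.

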C.3.b. Enrollment Session. Upon obtaining consent /assent, an enrollment session will be scheduled. At this session students' height and weight will be measured and they will complete an online enrollment survey addressing preferences, baseline characteristics, current habits, values, ethnic identity , their level of interest in making dietary changes and any changes they might wish to make. They will download the app and receive instruction in its use, including photo submission and rating foods on a Likert scale of very healthy to very unhealthy. They will be informed that they will be randomly assigned to use one of three versions of the app by the technology team who will apply to appropriate functionality to their app.

Ame00110293

Due to recruitment and enrollment efforts being conducted virtually because of the COVID-19 pandemic, participants will be guided as they take their own height and weight measurements. Since this will be done remotely, we will send any participants who require a scale, a tape measure, a square, and/or pencils, the necessary materials, which they will be able to keep.

Randomization – The technology team will randomly assign participants as they enroll to either the intervention or one of the control groups. They will then adjust the functionality of the app for the participants accordingly, and will send a message to their phone indicating their group assignment, along with instructions for their group. Thus, the research assistant who collects data will be blinded regarding group assignment.

C.3.c. Four Week Intervention

Week 1 – Student Registration of Eating Venues. Students will be asked to identify, using ActiPal, when they are in an eating venue (cafeteria, restaurant, or convenience store). The venue data (time and location) are registered

in PiLR. They will be encouraged to submit a photo of their food choices and annotate it with a rating on the very healthy to very unhealthy scale.²⁸ By the end of week 1 the system will have collected data about the most frequent eating locations, when they typically eat there, and what food they choose.

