Week 2 – Eating Venue Identification. We will use the system to identify and contact students when they are in eating venues. We will ask students via an EMA survey whether the system is correct. For erroneous detections the appropriate stored venue criteria (location, geofence, time of day or dwell time) will be adjusted to improve detection.³⁵ For correct detections they will be asked to report on their food choice.

Throughout the study students will be able to identify newly encountered eating venues. If the app does not recognize it, they will be asked to register that location (as they did in week 1). The first assessment of eating venue recognition accuracy will be calculated. Investigators will make an overall assessment of recognition criteria and potentially correlated factors such as neighborhood or which school the student attends.

Week 3 – Delivery of Location Linked Tailored Messages. In week 3 the system will try to deliver a relevant message when a student enters an eating venue with the intent to eat. EMA surveys will elicit whether messages are appropriate (i.e., received prior to making a choice, the venue is correct, the suggested food is available), relevant (i.e., suggestion matched their preferences), and if/how it influenced their choice. At the end of week 3 the feasibility and acceptability of location linked tailored texts will be demonstrated.

Week 4 – Inclusion of EMA Questions Including Feedback. During week 4 we will assess the feasibility and acceptability of including content that provides feedback on earlier choices. The EMA tool will be used to provide information from a recent choice and to request current information (e.g., students may be reminded of the health rating of their choice from the day before and asked whether there are healthier options available today). In addition, the EMA tool will be used to congratulate students for making healthier choices and for submitting the requested photos. Students will be asked to provide their perspectives as in week 3.

For this amendment weeks 1 to 3 will not be repeated. Participants will use the app for 6 months in one of 3 groups.

We have shortened our study period time frame from 6 months to 1 month due to the COVID-19 pandemic.

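### The visit model omits reported entry frequency of fast food restaurant visits, the only pre-randomisation measure of visiting, and so loses precision in the between-group level contrast

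*Combined protocol and SAP*

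**What the plan says.** **Entry (C.3.a).** Participants must be adolescents "with a BMI>85th percentile who eat at FFR at least 3 times/week". This sets a floor. No upper limit, mean or spread is given.

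**Enrolment data (C.3.b).** Participants complete an "online enrollment survey addressing preferences, baseline characteristics, current habits" and other items. FFR frequency is not named as an item.

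**Allocation (C.3.b).** The technology team will "randomly assign participants as they enroll to either the intervention or one of the control groups". No stratification is stated.

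**No run-in (C.3.c).** "For this amendment weeks 1 to 3 will not be repeated". Participants use their assigned version of the app throughout, for a period shortened to 1 month, so every app-recorded visit falls after randomisation.

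**Visit model (C.3.e).** The plan for visit counts reads: "we will fit a GEE Poisson regression model as a function of time, treatment group (intervention vs. control group 2 vs control group 3". A time-by-group interaction completes the model. The calorie model has the same form, with intervention against control group 2 only. The stated purpose is to compare trajectories between groups.

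**Covariates (C.3.e).** The secondary models add characteristics, given as examples: "extent of app use, initial BMI, and ethnic identity". The exploratory food-choice analysis lists sex, level of interest in change and BMI. Neither list names entry FFR frequency.

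**The concern.** The trial selects on a behaviour, measures the same behaviour as an outcome, and leaves the one pre-randomisation report of it out of every named model. Some participants will enter near the floor of 3 times a week and others above it. If those habits persist, they explain part of the variation in visits during the study. Unadjusted, that part stays in the error of any contrast of visit level between groups.

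This matters because Aim 3 asks whether app use goes with less frequent FFR visits, which is a question about level. Group features are active from the start and follow-up is 1 month. An effect that begins at once and holds steady would therefore appear as a difference in level, with little or no difference in slope. At stake are the width of the interval for that contrast and the planning information the pilot passes to the intended larger trial.

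**Working it through.** There is no stated figure to reproduce. The documents give no alpha, power, effect size, SD, visit rate or allocation ratio, and do not derive the 150. Every numerical input below is an assumption unless a section is named.

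**1. Which term can the covariate help?** Write the log mean visit rate for person *i* as a_i + β1·t + β2·g + β3·t·g, where a_i is the person's stable habitual level.
- β3 compares changes over time. A stable a_i cancels from a change, so entry frequency added as a main effect cannot sharpen β3.
- β2, or the average rate over follow-up, compares levels. There a_i remains in the error, and entry frequency can remove the part it predicts.

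**2. Size for the level contrast, by formula.** If ρ is the correlation between reported entry frequency and on-study visits among those enrolled, adjustment multiplies the variance by 1 − ρ².

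| ρ | 1 − ρ² | Variance removed | Standard error multiplied by √(1 − ρ²) |
|---|---|---|---|
| 0.3 | 0.91 | 9% | 0.95 |
| 0.5 | 0.75 | 25% | 0.87 |
| 0.7 | 0.51 | 49% | 0.71 |

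**3. What this could mean for power.** Assume 50 per arm ("We will recruit 150 13-17 year olds", read as a total split equally among three groups), two-sided 0.05 and a standardised difference of 0.4. Power = Φ(0.4·√(50/2)/√(1 − ρ²) − 1.96). Since 0.4·√25 = 2.0:
- unadjusted: Φ(2.00 − 1.96) = 0.52
- ρ = 0.3: Φ(2.10 − 1.96) = 0.55
- ρ = 0.5: Φ(2.31 − 1.96) = 0.64
- ρ = 0.7: Φ(2.80 − 1.96) = 0.80

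**4. Check in the planned type of model.** GEE Poisson with exchangeable correlation, two arms of 50, four weekly counts, entry frequency at least 3 per week, no treatment effect, 300 simulated trials per setting, fitted with and without log(entry frequency).

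| Observed correlation | SD of level estimate, unadjusted → adjusted | Variance ratio, level | SD of slope estimate, both models | Variance ratio, slope |
|---|---|---|---|---|
| 0.38 | 0.1014 → 0.0949 | 0.88 | 0.0428 | 1.00 |
| 0.57 | 0.1192 → 0.0957 | 0.65 | 0.0395 | 1.00 |
| 0.80 | 0.1459 → 0.0795 | 0.30 | 0.0361 | 1.00 |

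The level reductions of 12%, 35% and 70% are close to ρ² (0.38² = 14%, 0.57² = 32%, 0.80² = 64%). Unadjusted estimates averaged within 0.002 of zero for slope and 0.009 for level, so no material bias appears. If 150 means 150 per city, and so about 150 per arm, the one setting run gave ratios of 0.91 (level) and 1.00 (slope) at correlation 0.37.

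**5. Sensitivity.** Other simulated settings, with correlation measured after the 3-per-week floor was applied, removed:
- almost nothing at 0.19, and 3–6% at about 0.2
- 10–16% at 0.35, and 22–23% at about 0.4
- 23–34% at 0.5, and 28–38% at about 0.6

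The floor itself restricts the range. If the correlation is instead taken before applying it, the reductions were about 0% at 0.3, 3–15% at 0.5 and 27–35% at 0.7.

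**6. Can the slope term find an immediate effect?** With an assumed constant rate ratio of 0.8 from week 1, β3 is zero by construction. In simulation the time-by-group test rejected in 4–7% of trials, about the nominal 5%. The effect shows only in the level contrast.

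**The case against.** The strongest reply is that C.3.e sets out to compare trajectories, and the interaction carries that comparison. Stable differences between people cancel there, and the proposed covariate changes nothing. This stands in full for the slope. It does not settle the matter, because the same model contains a group term, Aim 3 is phrased in terms of level, and the slope is blind to an immediate, steady effect.

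Other parts of the reply also stand:
- A reader might infer that the groups are compared with bias. Allocation is random, and chance imbalance in habitual frequency is already reflected in the standard error. With the usual robust GEE errors, unadjusted inference remains valid.
- A reader might infer that large, known differences are being ignored. The documents give only a floor. Applying a floor needs only a yes or no, and nothing says the number is recorded.
- The secondary covariate list is open-ended, so adjustment is unplanned rather than ruled out.
- Entry frequency would be self-reported by adolescents, so a high correlation with app-recorded visits cannot be presumed.
- This is a pilot, and the models sit under a primary outcome headed as technological feasibility.

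**Conclusion.** The point holds as a loss of precision in one contrast. The visit model leaves out the only pre-randomisation measure of visiting that the described procedures can yield, and this widens the interval for the between-group difference in visit level. The gain from adjusting is zero for the time-by-group slope.

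For the level contrast, a fair summary is roughly 0–10% less variance at a correlation of 0.2–0.3, about 10–25% at 0.35–0.5, and about 25–50% at 0.6–0.7. Single simulated settings fall somewhat outside these bands. They rest on assumed correlations, spreads and per-arm numbers, none of which the documents supply.

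One might extend the finding to calories. The documents do not support that as it stands: C.3.e does not say whether calories are totalled per period or analysed per purchase, and no gain has been shown for calories per purchase. This is an inexpensive improvement to the analysis and not a defect that invalidates it.

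**What to change.** 1. In C.3.b, record FFR times per week as a number for every participant at enrolment, before randomisation. The survey already covers current habits. Once exposure has begun, the value could be recovered only by recall.
2. In C.3.e, pre-specify log(entry FFR times per week) as a covariate in the GEE Poisson visit model.
3. Report the adjusted contrast of average visit rate between groups, or a joint test of group and time by group, alongside the slope, and state in advance which is the test. If the group coefficient is used, state how time is coded, since that decides the time point it refers to.
4. State whether calories are totalled per period or analysed per purchase. Include the covariate in the calorie model only if they are totalled per period.

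The cost is one survey field and one degree of freedom. If self-reported frequency turns out to be weakly correlated with app-measured visits, little precision is gained, but the observed correlation would still be useful for planning the larger trial.
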